10.3.2 Reporting of serious adverse events

All SAEs will be reported, whether or not considered causally related to the investigational product, or to the study procedure(s).. Sponsor is responsible for informing the Health Authorities of the SAE as per local requirements.

After the initial notification of an AE or SAE, the investigator is required to follow up each case and obtain more data on the patient's state. All the AEs and SAEs documented in previous visits must be reviewed in subsequent visits. All AEs and SAEs must be monitored until their resolution, stabilization, explanation of the event by another cause, or until the follow-up period ends. This is applicable to all the patients, including those who withdraw early.

The investigator will include in the follow-up any additional research that may clarify the nature and/or causality of the AE or SAE. This might include additional laboratory tests or studies, histopathologic examinations, or the consultation of other healthcare professionals. Any co-investigator can ask the investigator to carry out additional evaluations to definitively clarify the nature and/or the causality of AEs or SAEs. If the patient dies while participating in the study or during a follow-up period agreed upon mutually, the investigator will provide a copy of any postmortem finding requested, including histopathology.

The sponsor is responsible for notifying all serious or unexpected AEs potentially related to the treatments being investigated that occur during the study to the AEMPS, competent bodies of the autonomous communities where the clinical trial is being conducted within the time frame established by Spanish law and will concurrently forward all such reports to [REDACTED]. A copy of the SAE report must be sent by e-mail to [REDACTED] at the time the event is reported to the Health Authorities [REDACTED]. It is the responsibility of the sponsor to compile all necessary information and ensure that the Health Authorities receives a report according to the reporting requirement timelines and to ensure that these reports are also submitted to [REDACTED] at the same time.

Clinical Study Protocol
Drug Substance DURVALUMAB/TREMELIMUMAB
Study Number ESR 15-11561-61-DUNE
EudraCT Nº: 2016-002858-20
Edition Number: 5.0 dated on June 09th, 2021

SAE report and accompanying cover page will be sent by way of email to

DEPARTAMENTO DE INVESTIGACIÓN [REDACTED]

Fax: [REDACTED]

Email: [REDACTED]

Clinical Study Protocol
 Drug Substance DURVALUMAB/TREMELIMUMAB
 Study Number ESR 15-11561-61-DUNE
 EudraCT Nº: 2016-002858-20
 Edition Number: 5.0 dated on June 09th, 2021

If a non-serious AE becomes serious, this and other relevant follow-up information must also be provided to [REDACTED] and the Health Authorities.

Serious adverse events that do not require expedited reporting to the Health Authorities still need to be reported [REDACTED] preferably using the MedDRA coding language for serious adverse events. This information should be reported on a monthly basis and under no circumstance less frequently than quarterly.

10.3.2.1 Reporting of deaths

All deaths that occur during the study, or within the protocol-defined 90-day post-last dose of durvalumab + tremelimumab safety follow-up period must be reported as follows:

- Death that is clearly the result of disease progression should be documented but should not be reported as an SAE.
- Where death is not due (or not clearly due) to progression of the disease under study, the AE causing the death must be reported to as a SAE within **24 hours** (see Section 10.3.2 for further details). The report should contain a comment regarding the co-involvement of progression of disease, if appropriate, and should assign main and contributory causes of death.
- Deaths with an unknown cause should always be reported as a SAE.

Deaths that occur following the protocol-defined 90-day post-last-dose of durvalumab safety follow-up period will be documented as events for survival analysis, but will not be reported as an SAE.

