10.3.1 Study recording period and follow-up for adverse events and serious adverse events

Adverse events and serious adverse events will be recorded from time of signature of informed consent, throughout the treatment period and including the follow-up period (90 days after the last dose of durvalumab + tremelimumab).

During the course of the study all AEs and SAEs should be proactively followed up for each subject. Every effort should be made to obtain a resolution for all events, even if the events continue after discontinuation/study completion.

If a subject discontinues from treatment for reasons other than disease progression, and therefore continues to have tumor assessments, drug or procedure-related SAEs must be captured until the patient is considered to have confirmed PD and will have no further tumor assessments.

The investigator is responsible for following all SAEs until resolution, until the subject returns to

Clinical Study Protocol
Drug Substance DURVALUMAB/TREMELIMUMAB
Study Number ESR 15-11561-61-DUNE
EudraCT Nº: 2016-002858-20
Edition Number: 5.0 dated on June 09th, 2021

baseline status, or until the condition has stabilized with the expectation that it will remain chronic, even if this extends beyond study participation.

Follow-up of unresolved adverse events

Any AEs that are unresolved at the subject's last visit in the study are followed up by the investigator for as long as medically indicated, but without further recording in the eCRF. After 90 days, only subjects with ongoing investigational product-related SAEs will continue to be followed for safety.

The sponsor and [REDACTED] retain the right to request additional information for any subject with ongoing AE(s)/SAE(s) at the end of the study, if judged necessary.

Post study events

After the subject has been permanently withdrawn from the study, there is no obligation for the investigator to actively report information on new AE or SAEs occurring in former study subjects after the 90-day safety follow-up period for patients treated with durvalumab + tremelimumab. However, if an investigator learns of any SAEs, including death, at any time after the subject has been permanently withdrawn from study, and he/she considers there is a reasonable possibility that the event is related to study treatment, the investigator should notify the study sponsor, who will inform [REDACTED] Drug Safety.

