	Day (±3)	Months (±1 week)						12 Months and every 6 Months (±2 weeks)
		30	2	3	4	6	8	
Physical examination ^a	x	x	x	x	x	x	x	
Vital signs (temperature, respiratory rate, blood, pressure, pulse)	x	x	x	x	x	x	x	
Weight	x	x	x	x	x	x	x	
Urine hCG or serum βhCG	x							
AE/SAE assessment	x	x	x					
Concomitant medications	x	x	x					
Palliative radiotherapy	As clinically indicated							
ECOG performance status	x	x	x		x (and month 9)			x
Subsequent anti/cancer therapy	x	x	x	x	x	x	x	
Survival status: phone contact with subjects who refuse to return for evaluations and agree to be		x	x	x	x	x	x	x (every 2 months)

Clinical Study Protocol
 Drug Substance DURVALUMAB/TREMELIMUMAB
 Study Number ESR 15-11561-61-DUNE
 EudraCT N°: 2016-002858-20
 Edition Number: 5.0 dated on June 09th, 2021

contacted							
Hematology	x	Every 8-12 weeks, according to investigator's criteria					x
Serum chemistry	x	Every 8-12 weeks, according to investigator's criteria					
Thyroid function tests (TSH, and fT3 and fT4) ^b	x	Every 8-12 weeks, according to investigator's criteria					
SPD-L1 concentration (to assess target engagement)		x					
Tumour assessment (CT or MRI)	
For subjects who achieve disease control following 12 months of treatment, tumour assessments should be performed every 12 weeks relative to the date of first infusion thereafter until confirmed PD by RECIST 1.1 by investigational site review. Please refer to SCHEDULE OF STUDY ASSESSMENTS for timings of confirmatory scans.
 
For subjects who discontinue study drug due to toxicity (or symptomatic deterioration), tumour assessments should be performed relative to the date of first infusion as follows: every 12 weeks until confirmed PD by RECIST 1.1 by investigational site review. Please refer to SCHEDULE OF STUDY ASSESSMENTS for timings of confirmatory scans.
 
Upon confirmed PD, scans should be conducted according to local standard clinical practice until a new treatment is started (these scans are optional).
						
^a Full physical exam ^b Free T3 and free T4 will only be measured if TSH is abnormal. They should also be measured if there is clinical suspicion of an adverse event related to the endocrine system. ^c For patient questionnaires different approaches based on indication and study design.							

Appendix 3 Schedule of study procedures: follow-up for subjects who have discontinued durvalumab or tremelimumab treatment due to confirmed progression of disease at the investigator discretion

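### Section 10.3.2.1 excludes deaths beyond 90 days after the last dose from SAE reporting, against Section 10.3.1 and its own opening rules, so a late related death could be logged as a survival event only

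*Protocol*

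**What the plan says.** Section 10.3.2.1 (Reporting of deaths) contains three statements that bear on late deaths:

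- Its opening sentence sets the scope: "All deaths that occur during the study, or within the protocol-defined 90-day post-last dose of durvalumab + tremelimumab safety follow-up period must be reported".
- One of its bullets reads: "Deaths with an unknown cause should always be reported as a SAE".
- Its closing sentence, on deaths after the 90-day period, says that they "will be documented as events for survival analysis, but will not be reported as an SAE".

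Section 10.3.1 sets the general recording window at 90 days after the last dose and then adds three further rules:

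- For patients who stop treatment for a reason other than progression, "drug or procedure-related SAEs must be captured until the patient is considered to have confirmed PD and will have no further tumor assessments".
- Under the paragraph on unresolved events: "After 90 days, only subjects with ongoing investigational product-related SAEs will continue to be followed for safety".
- Under the paragraph on post-study events, "if an investigator learns of any SAEs, including death, at any time after the subject has been permanently withdrawn from study" and considers it possibly related, the sponsor should be notified.

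Section 10.1.2 defines an SAE as arising in any study phase, follow-up included, with death as the first criterion. Section 10.3.2 says that all SAEs are reported regardless of causality. Section 8.1.3 keeps every patient in survival follow-up to the end of the study. Appendix 2 is the follow-up schedule for patients who completed treatment with disease control or stopped for toxicity without confirmed progression. It marks "AE/SAE assessment" at day 30 and months 2 and 3 only, while tumour assessments continue every 12 weeks until confirmed progression.

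**The concern.** The closing sentence of Section 10.3.2.1 is unconditional, and other rules in the same chapter require the opposite for some of the deaths it covers. Staff handling a late death are likely to turn to the section on reporting deaths and to find there an instruction not to file an SAE.

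The safety profile is a secondary objective (Section 2.2). Patients who stopped for toxicity are those in whom a late immune-mediated death is of most interest. The table of expected reactions for the combination in Section 1.4.2.3 treats every fatal event as unexpected for reporting purposes. A related death that is not filed as an SAE may therefore also miss expedited review by the sponsor and the authorities.

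**Working it through.** No sample size, power or error rate is involved, and Sections 10.3.1 and 10.3.2.1 agree on the 90-day figure. The check is textual: take each kind of death after day 90 and ask what each rule requires.

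**Can a death be both within the study and past day 90?** Yes. Survival follow-up runs to the end of the study (Section 8.1.3). Section 13.6 places the last patient's entry in December 2019 and the last visit in December 2021, which is 24 months. With about 12 months of treatment (Section 3.1), 24 − 12 = about 12 months remain after treatment even for the last patient enrolled.

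**Case 1: treatment stopped for toxicity, no confirmed progression, still in follow-up, death judged drug-related.**
- Section 10.3.1, until-progression rule: capture as a related SAE.
- Section 10.3.2.1, opening sentence and the bullet on deaths not clearly due to progression: report as an SAE within 24 hours.
- Sections 10.1.2 and 10.3.2: an SAE, to be reported.
- Section 10.3.2.1, closing sentence: not reported as an SAE.
- Post-study paragraph: does not apply, because the patient has not been withdrawn from the study.

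This is a direct contradiction.

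**Case 2: the same patient, cause of death unknown.** The unknown-cause bullet makes it an SAE without exception; the closing sentence says it is not one. The contradiction lies within a single section.

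**Case 3: confirmed progression, in survival follow-up, death not clearly due to progression.** The until-progression rule has ended and the patient has not been withdrawn, so neither Section 10.3.1 rule applies. The opening sentence of Section 10.3.2.1 covers the death as one during the study; the closing sentence excludes it.

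**Case 4: permanently withdrawn from the study, possibly related death.** The investigator who learns of it should notify the sponsor, at any time. The closing sentence does not forbid notification, but it does not refer to it and says that the death is not reported as an SAE.

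**Case 5: death clearly due to progression.** All rules agree that it is not an SAE. There is no conflict.

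**Schedule.** The until-progression rule has no time limit, but the AE/SAE row of Appendix 2 ends at month 3. The 12-weekly scans that continue to confirmed progression are contacts at which related events could be asked about, and the schedule does not ask.

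**The case against.** The strongest defence is that the closing sentence has to be read with the rest of the chapter. The section's opening already covers deaths during the study. Section 10.3.2.1 reports the adverse event that caused the death rather than the death itself, so the causal event could still be captured under Section 10.3.1 while the death is counted for survival. Appendix 2 continues physical examination, vital signs, laboratory tests and scans beyond month 3, so a serious immune event would probably come to the site's notice. The main schedule also appears to carry an AE/SAE mark in its follow-up column.

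Part of this stands. A harmonising reading is possible, and it is why the consequence is that a late related death could go unreported as an SAE, not that it will. But the closing sentence does not say that the causal event stays reportable, and it makes no exception. Continued visits help a site to learn of an event; they do not settle how the site should classify it. The main schedule refers follow-up to Appendices 2 and 3, and its AE footnote limits AE collection to 28 days after the last dose, so it mitigates the point without resolving it.

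Three stronger readings are tempting and are not supported:

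- A reader might infer that the post-study paragraph makes the Case 1 death reportable. It covers only patients permanently withdrawn from the study, depends on the investigator learning of the event, and asks for notification in terms of what should be done.
- A reader might infer that the sentence limiting follow-up after 90 days cancels the until-progression rule. It stands in the paragraph on unresolved events and can be read as governing only how long known events are followed.
- A reader might infer that late events are kept out of the safety tables. The safety tables in the SAP set no 90-day limit, and two of them are titled as covering follow-up, so late events that are captured are not excluded.

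**Conclusion.** The point holds as an internal contradiction in safety reporting. The closing sentence of Section 10.3.2.1 cannot be followed literally together with the until-progression rule of Section 10.3.1, or with that section's own opening sentence and unknown-cause bullet. The possible harm is an understated count of fatal related toxicity and slower safety review. The primary and survival endpoints are not affected.

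The size cannot be stated, because the documents give no rate of new related SAEs or deaths beyond 90 days. A reader might take the roughly 15% permanent discontinuation for AEs in Section 1.4.2.3 and infer 0.15 × 126 = 18.9, about 19 patients. If each stopped at month 2, AE/SAE checks would end near month 5 (2 + 3), leaving 9 − 5 = 4 to 12 − 5 = 7 months without a scheduled check. That is an illustration, not an estimate. The rate is pooled from other studies, the month-2 stop is assumed, and the gap exists only for patients who remain progression-free. With the progression-free proportions of 30% to 50% at 9 months from Section 11.3, cohorts 1 to 3 (93 patients) would give 0.15 × 93 = 13.95, of whom 0.30 × 13.95 = 4.2 to 0.50 × 13.95 = 7.0 reach month 9, still with the month-2 stop assumed. These are patients exposed to the gap, not events missed.

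**What to change.** Reconcile Sections 10.3.1 and 10.3.2.1:

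- Qualify the closing sentence of Section 10.3.2.1 so that it does not override the capture of related SAEs until confirmed progression or the post-study notification rule, and state how it fits with the section's opening sentence and its unknown-cause bullet.
- In Section 10.3.1, make clear that the sentence limiting safety follow-up after 90 days concerns events already known.
- In Appendix 2, extend the AE/SAE row beyond month 3 to confirmed progression, limited to related SAEs, at the existing 12-weekly tumour-assessment contacts.

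No new table is needed in the SAP. The cost is protocol wording and one row in an existing schedule, with no added visits. The downside is a few more SAE reports.

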10.3.3 Other events requiring reporting

10.3.3.1 Overdose

An overdose is defined as a subject receiving a dose of durvalumab + tremelimumab in excess of that specified in the Investigator's Brochure, unless otherwise specified in this protocol.

Any overdose of a study subject with durvalumab + tremelimumab, with or without associated AEs/SAEs, is required to be reported within 24 hours of knowledge of the event to the sponsor, who will send a copy to [REDACTED] Patient Safety, or designed using the designated Safety e-mailbox (see Section 10.3.2 for contact information). If the overdose results in an AE, the AE must also be recorded as an AE (see Section 10.3). Overdose does not automatically make an AE serious, but if the consequences of the overdose are serious, for example death or hospitalization, the event is serious and must be recorded and reported as an SAE (see Section 10.3 and Section 10.3.2). There is currently no specific treatment in the event of an overdose of durvalumab or tremelimumab.

The investigator will use clinical judgment to treat any overdose.

10.3.3.2 Hepatic function abnormality

Hepatic function abnormality (as defined in Section 10.1.3.) in a study subject, with or without associated clinical manifestations, is required to be reported as "hepatic function abnormal" **within 24 hours of knowledge of the event** to the sponsor, who will send a copy to [REDACTED] Patient Safety, using the designated Safety e-mailbox (see Section 10.3.2 for contact information), unless a definitive underlying diagnosis for the abnormality (e.g.,

Clinical Study Protocol
 Drug Substance DURVALUMAB/TREMELIMUMAB
 Study Number ESR 15-11561-61-DUNE
 EudraCT Nº: 2016-002858-20
 Edition Number: 5.0 dated on June 09th, 2021

cholelithiasis or bile duct obstruction) that is unrelated to investigational product has been confirmed.

- If the definitive underlying diagnosis for the abnormality has been established and is unrelated to investigational product, the decision to continue dosing of the study subject will be based on the clinical judgment of the investigator.
- If no definitive underlying diagnosis for the abnormality is established, dosing of the study subject must be interrupted immediately. Follow-up investigations and inquiries must be initiated by the investigational site without delay.

Grade 1-2 events should be considered AEs, not SAEs. However, Grade 1-2 events should be reported as SAEs if requires hospitalization or if they are medically important events based on the investigator judgement.

Grade 3 events, should be reported as SAE if requires hospitalization or if they are medically important events based on the investigator judgement.

All grade 4 events should be reported as SAEs.

Cases where a patient shows elevations in liver biochemistry may require further evaluation and occurrences of AST or ALT $\geq 3 \times$ ULN together with total bilirubin $\geq 2 \times$ ULN may need to be reported as SAEs.

Each reported event of hepatic function abnormality will be followed by the investigator and evaluated by the sponsor.

10.3.3.3 Pregnancy

a) Maternal exposure

If a patient becomes pregnant during the course of the study, the IPs should be discontinued immediately.

Pregnancy itself is not regarded as an AE unless there is a suspicion that the IP under study may have interfered with the effectiveness of a contraceptive medication. Congenital abnormalities or birth defects and spontaneous miscarriages should be reported and handled as SAEs. Elective abortions without complications should not be handled as Aes. The outcome of all pregnancies (spontaneous miscarriage, elective termination, ectopic pregnancy, normal birth, or congenital abnormality) should be followed up and documented even if the patient was discontinued from the study.

If any pregnancy occurs in the course of the study, then the Investigator or other site personnel should inform the appropriate sponsor representatives within 1 day, ie, immediately, but **no later than 24 hours** of when he or she becomes aware of it.

The designated sponsor representative will work with the Investigator to ensure that all relevant information is provided to the sponsor, who will inform [REDACTED] Patient Safety data entry site. The same timelines apply when outcome information is available.

b) Paternal exposure

Male patients should refrain from fathering a child or donating sperm during the study and for 180 days after the last dose of durvalumab + tremelimumab combination therapy or 90 days after the last dose of durvalumab monotherapy, whichever is the longer time period.

Clinical Study Protocol
 Drug Substance DURVALUMAB/TREMELIMUMAB
 Study Number ESR 15-11561-61-DUNE
 EudraCT N°: 2016-002858-20
 Edition Number: 5.0 dated on June 09th, 2021

Pregnancy of the patient's partner is not considered to be an AE. However, the outcome of all pregnancies (spontaneous miscarriage, elective termination, ectopic pregnancy, normal birth, or congenital abnormality) occurring from the date of the first dose until 90 days after the last dose should, if possible, be followed up and documented.

Where a report of pregnancy is received, prior to obtaining information about the pregnancy, the Investigator must obtain the consent of the patient's partner. Therefore, the local study team should adopt the generic ICF template in line with local procedures and submit it to the relevant Ethics Committees (ECs) prior to use.

11. STATISTICAL METHODS AND SAMPLE SIZE DETERMINATION

11.1. Description of analysis sets

The statistical analyses described in this section will be performed as further outlined in the Statistical Analysis Plan, which will be included in the clinical study report for this protocol.

Analysis Sets

The analysis sets will be defined as follows:

- **Full Analysis Set** will include all allocated subjects. This will be primary analysis set for the efficacy endpoints.
- **Per Protocol Analysis Set** will include those subjects who were allocated and received at least one dose of the assigned study drug and had no major protocol deviations. The subjects will complete both baseline and at least one post-baseline tumor assessments (week 12).
- **Safety Analysis Set** will include all subjects who were allocated and received at least one dose of the study drug and had at least one post-baseline safety evaluation (week 12). This will be the analysis set for all safety evaluations.
- **Pharmacodynamic Analysis Set**: All the subjects who have received at least one dose of study drug and have evaluable pharmacodynamic data.

Demographic and other baseline characteristics

Demographic and other baseline characteristics will be summarized and listed. For continuous demographic/baseline variables including age, weight, and vital signs, results will be summarized and presented as n, number of not available data (NA), mean, standard deviation, median, and minimum and maximum values. For categorical variables such as race/ethnicity, the number and percentage of subjects will be used.

Prior and concomitant medications

Concomitant medications will be assigned an 11-digit code using the World Health Organization Drug Dictionary (WHO DD) drug codes. Concomitant medications will be further coded to the appropriate Anatomical-Therapeutic-Chemical (ATC) code indicating therapeutic classification. Prior and concomitant medications will be summarized and listed by drug and drug class.

Efficacy Analyses

All efficacy analyses will be based primarily on the Full Analysis Set and secondarily on the Per

Clinical Study Protocol
 Drug Substance DURVALUMAB/TREMELIMUMAB
 Study Number ESR 15-11561-61-DUNE
 EudraCT Nº: 2016-002858-20
 Edition Number: 5.0 dated on June 09th, 2021

Protocol Analysis Set.

Data cut-off for the primary study analysis will happen following after the last patient included in the study has performed the first tumor evaluation (week 12 after first dose of study drug). The following tumor evaluations will take place every 12 weeks until documentation of disease progression or start of another anticancer therapy.

Analysis of primary efficacy variable

The analysis of clinical benefit rate and overall survival rate will be performed independently for each study cohort when the last patient included in the corresponding cohort of the study will arrived to 9 months after inclusion in the study or have progressed. The primary objective of the study will be based on the investigator assessment.

